#### **List of Abbreviations**

AE Adverse Event

ANCOVA Analysis of Covariance

BP Blood Pressure

CRF Case Report Form (electronic/paper)

CSA Clinical Study Agreement
CTC Common Toxicity Criteria

CTCAE Common Terminology Criteria for Adverse Event

DAE Discontinuation due to Adverse Event

DT Dopaminergic Treatment

EC Ethics Committee

GCP Good Clinical Practice

IB Investigator's Brochure

ICF Informed Consent Form

ICH International Conference on Harmonization

IND Investigational New Drug

IP Investigational Product (includes active comparator and placebo)

ITT Intention to treat

MDS-UPDRS Movement Disorders Unified Parkinson's Disease Rating Scale

NMSQ Non-Motor Symptoms Questionnaire

NMSS Non-Motor Symptom assessment scale for Parkinson's Disease

MoCA Montreal Cognitive Assessment

NAD Nicotinamide Adenine Dinucleotide

NR Nicotinamide Riboside
PD Parkinson's Disease
SAE Serious Adverse Event

SD Stable Disease

SOP Standard Operating Procedure

Confidential Page 5 of 21

#### 1 Introduction

This document has been written based on the study protocol, Version 6.0.

Affecting 1-2% of the population over the age of 65, Parkinson's disease (PD) is a major cause of death and disability with a devastating global socioeconomic impact. In Europe alone, PD affects an estimated 1.2 million people at a cost of €14 billion per year. Current treatments for PD are symptomatic and have no impact on disease progression. As a result, patients face a future of progressive disability, early institutionalization and premature death.

# 1.1 Background and Rationale

Previous research has shown that nicotinamide riboside (NR) holds promise as a potential neuroprotective, disease-modifying therapy for PD (see Study Protocol Section 1.3/1.4).

NOPARK aims to determine whether daily oral administration of NR will slow/inhibit the progression of PD. See the study protocol for more details on the background and rationale of the NOPARK study.

# 1.2 Objectives and Endpoints

The NOPARK study investigates the hypothesis that oral administration of NR can ameliorate neuronal metabolism, increase neuronal resilience, and inhibit neurodegeneration, resulting in amelioration of clinical symptoms and delayed PD progression. Primary and secondary endpoints are listed in Table 1.

Table 1 Objectives and related endpoints

	Objective	Endpoint
Primary	To compare the effectiveness of orally administered nicotinamide riboside (NR) 500 mg twice per day versus placebo on delaying disease progression in PD.	Change from baseline in MDS-UPDRS Total Score (sum of parts I, II and III) in the ON-medication state at week 52.
Key secondary	To compare the effectiveness of orally administered nicotinamide riboside (NR) 500 mg twice per day versus placebo on delaying the progression of motor symptoms in PD.	Change from baseline in the MDS- UPDRS Part III in the ON-medication state at Week 52.
	To compare the effectiveness of orally administered nicotinamide riboside (NR) 500 mg twice per day versus placebo on delaying the progression of dopaminergic nigrostriatal denervation in PD.	Change from baseline in the mean striatal binding ratio (SBR) of the putamen, bilaterally, as measured [1231]FP-CIT Single-Photon Emission Computed Tomography (SPECT) Imaging of the Dopamine Transporter (DaT, DaTscan) at Week 52.
	To compare the effectiveness of orally administered nicotinamide riboside (NR) 500 mg twice per day versus placebo on delaying the progression	Change from baseline in the MDS-UPDRS Part I in the ON-medication state at Week 52.

Confidential Page 6 of 21

	Objective	Endpoint
	of non-motor symptoms in daily living in PD.	
	To compare the effectiveness of orally administered nicotinamide riboside (NR) 500 mg twice per day versus placebo on delaying the progression of motor aspects of experiences of daily living in PD.	Change from baseline in the MDS- UPDRS Part II in the ON-medication state at Week 52.
	To compare the effect of orally administered nicotinamide riboside (NR) 500 mg twice per day versus placebo on the progression of nonmotor symptoms in PD.	Change from baseline in the NMSS Score in the ON-medication state at Week 52.
Other secondary	To compare the effect of orally administered nicotinamide riboside (NR) 500 mg twice per day versus placebo on the progression of cognitive dysfunction in PD.	Change from baseline in the MoCA score in the ON-medication state at Week 52.
	To compare the effect of orally administered nicotinamide riboside (NR) 500 mg twice per day versus placebo on quality of life in PD.	Change from baseline in the EQ-5D-5L index value, at week 52.
	To compare the effect of orally administered nicotinamide riboside (NR) 500 mg twice per day versus placebo on the progression of Hoehn and Yahr stage.	Hoehn and Yahr stage at Week 52.
Exploratory	To compare the effect of orally administered nicotinamide riboside (NR) 500 mg twice per day versus placebo on brain NAD levels in PD.	Change from baseline in brain NAD/ATP-α ratio measured by 31 Phosphorus magnetic resonance spectroscopy (31P-MRS) in the posterior brain (encompassing the occipital, parietooccipital and posterior parts of the temporal cortex), at 52 weeks between participants according to treatment allocation.
	To compare the effect of orally administered nicotinamide riboside (NR) 500 mg twice per day versus placebo on systemic NAD metabolism	Comparison of the change from baseline in the NAD metabolome in whole blood, measured by liquid chromatography mass spectrometry (LC-MS), at 52 weeks between participants according to treatment allocation.
	To compare the effect of orally administered nicotinamide riboside (NR) 500 mg twice per day versus placebo on neuronal damage	Comparison of the change from baseline in serum neurofilament light-chain (NfL) levels, measured by Simoa analysis, at 52 weeks between participants according to treatment allocation.
Safety	To determine whether NR is safe and well tolerated.	Report of all Adverse Events (AE) of moderate or severe intensity and Serious Adverse Events (SAE).

Confidential Page 7 of 21

### 1.3 Primary objective and endpoint

The primary endpoint is measured by MDS-UPDRS Total Score (Sum of Part I, II and III). The MDS-UPDRS is a questionnaire developed to evaluate non-motor and motor experiences of daily living and motor complications in PD. Higher scores indicate more severe symptoms of PD. For more information see Section 5.1.

## 1.4 Secondary objectives and endpoints

Key and other secondary endpoints are listed in Table 1. For further details on the definition of the endpoints, see Section 5.1.

#### 1.5 Exploratory objectives and endpoints

Exploratory endpoints are listed in Table 1. For further details on the definition of the endpoints, see Section 5.1.

#### 1.6 Safety

Recording AE and SAE will begin after baseline (week 0) and continue to be monitored and registered throughout the duration of the study up until 7 days after last study visit.

#### Adverse Event (AE)

An AE is any untoward medical occurrence in a patient administered a pharmaceutical product and which does not necessarily have a causal relationship with the treatment. An AE can therefore be any unfavorable and unintended sign, symptom, or disease temporally associated with the use of an investigational product, whether or not related to the investigational product.

If a patient has experienced AE(s), the following information will be recorded:

- The nature of the event described by precise standard medical terminology.
- The duration of the event (event onset and event end date; resolved/still ongoing).
- The intensity of the adverse event: Only intensity 2 (moderate) and 3 (severe) is registered as AE in eCRF.
- The causal relationship of the event to the study medication
- The outcome of the AE.
- The action taken.

#### Table 2 Definition of causal relationship and intensity in AEs.

Causal relationship:

 Unrelated: No temporal relationship to investigational product administration or a reasonable causal relationship between the AE and nonIntensity:

1. **Mild**: An event that is easily tolerated by the participant, causing minimal

Confidential Page 8 of 21

investigational product, concurrent disease, or circumstance.

- Unlikely: A temporal relationship to investigational product administration without a reasonable causal relationship to the AE.
- Possible: A reasonable causal relationship to the investigational product. Dechallenge information is lacking or unclear.
- Probable: A reasonable causal relationship to the investigational product. The event responds to dechallenge. Rechallenge is not required.
- Definite: A reasonable causal relationship to the investigational product.

- discomfort and not interfering with everyday activities.
- Moderate: An event that causes sufficient discomfort to interfere with normal everyday activities.
- 3. **Severe**: An event that prevents normal everyday activities. An AE that is assessed as severe should not be confused with an SAE. Severe is a category utilized for rating the intensity of an event; and both AEs and SAEs can be assessed as severe.

# Serious Adverse Event (SAE)

A SAE is any untoward medical occurrence that at any dose:

- Results in death.
- Is immediately life-threatening.
- Requires in-patient hospitalization or prolongation of existing hospitalization.
- Results in persistent or significant disability or incapacity.
- Is a congenital abnormality or birth defect.
- Is an important medical event that may jeopardize the subject or may require medical intervention to prevent one of the outcomes listed above.

Hospitalization for administrative reasons (for observation or social reasons) is allowed at the investigator's discretion and will not qualify as serious unless there is an associated adverse event warranting hospitalization.

#### 2 Study methods

# 2.1 Trial design

NOPARK is a national, multicenter, randomized, double-blinded, placebo controlled, phase 3 trial of oral NR supplementation in patients with PD. Patients are screened and randomized either to NR or placebo group and followed-up 52 weeks after baseline.

#### 2.2 Randomization

Randomization is done upon enrolment to the study. Patients are randomized in a 1:1 ratio to Placebo or NR stratified by site.

Confidential Page 9 of 21

### 2.3 Sample Size

For sample size calculation we assume a common standard deviation of 16 points in the total MDS-UPDRS (parts I, II and III) and an overall type 1 error rate of 5%. Such a standard deviation was seen in Holden et al (2018). This estimate is further supported by a blinded sample size review performed on a blinded data export from August 23, 2024. A sample size of 162 participants per group gives an 80% power given a difference of 5 points in the total MDS-UPDRS at 52 weeks between the NR and the placebo group (324 in total). A difference of this magnitude was reported to be within the clinically meaningful range (see Wyman-Chick et al (2018)). Accounting for approx. 20% drop out, 200 participants per group (400 in total) are required.

#### 2.4 Framework

Unless stated otherwise, all endpoints are tested for superiority of NR over placebo.

## 2.5 Statistical Interim Analyses and Stopping Guidance

No interim analyses are planned.

The whole trial may be discontinued at the discretion of the PI or the sponsor in the event of any of the following:

- Occurrence of AEs unknown to date in respect of their nature, severity and duration.
- Medical or ethical reasons affecting the continued performance of the trial.
- Difficulties in the recruitment of patients.

The sponsor and principal investigator will inform all investigators and the Ethics Committees of the termination of the trial along with the reasons for such action. If the study is terminated early on grounds of safety and Ethics Committees will be informed within 15 days.

#### 2.6 Timing of the Final Analysis

The final analysis will take place when all outcomes have been collected and the database is locked.

#### 2.7 Timing of Outcome Assessments

Data is collected over a period of 52 weeks with multiple measurement points (see Table 2). Patients must be on stable dopaminergic treatment at Baseline (see Study Protocol, Section 5.4). When the patient is on stable dopaminergic treatment (DT), screening (up to 3 months) is completed and the patient can join the study. DatScan and MRI should be performed within 6 weeks prior to Baseline and 2 weeks prior to the 52 weeks visit.

Confidential Page 10 of 21

Table 3 Trial flow chart

	Screening Period Treatment period		End of study					
Time	First screening	Last screening	Baseline	W4	W13	W26	W39	W52
Stable DT	Х	X						Х
MDS Clinical diagnosis Criteria (MDS CDC)			Х					
Inclusion/exclusion Evaluation	Х		Х					
Informed consent biobank, optional			Х					
Anamnestic information 	Х		Х					
Physical Examination	Х							
Concomitant medication	Х		Х		Х	Х	Х	Х
Medical history	Х		Х					
DatScan/MRI			Х					Х
Vital signs: BP, pulse, weight; height (Baseline)			Х		Х	Х	Х	Х
MDS-UPDRS			Х		Х	Х	Χ	Х
NMSS & NMSQ			Х			Х		Х
MOCA			Х					Х
EQ-5D-5L			Х					Х
Blood samples 			Х		Χ	Χ	Χ	Х
PBMC 			Х			Χ		Х
Treatment dispensation			X		(X) 	(X) 	(X) 	
Adverse event			Х	Х	Χ	Х	Χ	Х

# 3 Statistical Principles

## 3.1 Confidence intervals and p-values

Unless specified otherwise, all tests will be performed two-sided on a significance level of 5%. Consequently, confidence intervals (CI) will be reported with 95% confidence level.

Confidential Page 11 of 21

<sup>1Includes: family history of neurological illness, smoking history, anamnestic months since first clinical PD symptoms, occurrence and duration of REM sleep behaviour disorder symptoms, occurrence and duration of loss of smell.

<sup>2 CRP, ALAT, ASAT, GT, bilirubin, ALP, creatinine, urea, RBC, Hb, WBC with differential, platelets, CK, FT4, TSH, B12, folic acid, homocysteine, methylmalonic acid, sodium, potassium.

<sup>3 PBMC analysis is discontinued for new patients enrolled after 16.04.23. Patients enrolled before 16.04.23 will complete PBMC as described.

<sup>4 If necessary to resupply.

### 3.2 Adherence and protocol deviations

Adherence to the study protocol is monitored. All significant protocol deviations will be recorded in the trial data base. Procedures are detailed in the Protocol Deviation Handling Plan provided in the appendix.

#### 3.3 Analysis populations

The primary analysis will follow the intention-to-treat (ITT) principle. The **ITT population** contains all randomized patients with at least two post-baseline measurements, regardless of protocol adherence.

The **safety population** contains all enrolled patients with treatment as actually received.

In a secondary **per-protocol analysis set**, participants are excluded if any of the following apply:

- Failure to meet eligibility criteria
- Incorrect randomization
- Missing primary outcome at any visit
- Treatment compliance < 90%

- Change in standard-of-care PD regimen during the trial

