#### 5.2 Analysis methods

#### Primary endpoint analysis

The primary endpoint, the MDS-UPDRS changes from baseline to week 52 between the NR and placebo group, will be analyzed using Gaussian linear models for repeated measures (MMRM) with intervention, center, time (week 13, 26, 39, and 52), and intervention-by-time interaction as factors, and baseline MDS-UPDRS score as covariate. Centers with fewer than 20 patients are pooled into one center. The error terms are assumed to follow a multivariate normal distribution with unstructured covariance. Least square mean changes for both groups as well as the difference between the least squares treatment group means will be reported with 95% CIs and p-value testing the null hypothesis of no treatment effect.

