### 5.3 Missing data

While the MMRM model described above is robust to a certain extent to missing data (in particular when missing at random (MAR)), a sensitivity analysis using multiple imputation will be conducted to assess the robustness of the results. For this purpose, reference based multiple imputation will be performed using the R package *rbmi* (without MAR assumption).

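### The primary ITT population leaves out randomised patients with fewer than two post-baseline measurements, so the confirmatory test is not intention-to-treat and early dropout can bias it

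*SAP*

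**What the plan says.** SAP section 3.3 opens with the principle: "The primary analysis will follow the intention-to-treat (ITT) principle". The next sentence defines the ITT population as the set that "contains all randomized patients with at least two post-baseline measurements, regardless of protocol adherence".

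The primary model in section 5.2 is an MMRM with "time (week 13, 26, 39, and 52), and intervention-by-time interaction as factors", adjusted for center and baseline score. On the covariance it says: "The error terms are assumed to follow a multivariate normal distribution with unstructured covariance". Section 5.2 also tests the key secondary endpoints only if the primary endpoint is significant.

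Section 5.3 relies on the MMRM being reasonably robust when data are missing at random. It adds that "a sensitivity analysis using multiple imputation will be conducted to assess the robustness of the results", by a reference-based method, and names no analysis set for it.

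The appendix on protocol deviations uses a Full Analysis Set (FAS) that section 3.3 does not define. That FAS keeps patients who lack the MDS-UPDRS total at a visit and drops those incorrectly randomised.

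**The concern.** Membership of the primary set depends on something that happens after randomisation. Three consequences follow.

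- A patient seen at Week 13 who then leaves is removed. An MMRM accepts a single post-baseline value. Under missing-at-random, that value tells the model how the patient was doing before leaving, so the rule deletes the data on which section 5.3 relies.
- Read literally, a patient who missed Weeks 13, 26 and 39 but attended Week 52 is removed, although the primary endpoint was observed.
- If the reference-based imputation is run on the same set, the earliest dropouts are never imputed, and they are the patients for whom the imputation matters most.

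Early leaving may differ between arms, for example intolerance on NR and lack of benefit on placebo. If the patients removed differ in outcome between arms, the comparison is no longer the randomised one. The distortion sits in the confirmatory test and passes through the gate to the key secondary tests.

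**Working it through.** **1. Sample size (section 2.3).** The SAP writes "we assume a common standard deviation of 16 points in the total MDS-UPDRS" and "A sample size of 162 participants per group gives an 80% power given a difference of 5 points in the total MDS-UPDRS at 52 weeks". With a two-sided 5% test, n = 2 × (1.96 + 0.84)² × 16² / 5² gives 161 per group by the normal approximation. The t-test gives 161.7, so 162, with power 80.1%. For dropout, 162 / 0.80 = 202.5, so 203. The stated 200 corresponds to 1 − 162/200 = 19%, which fits approximately 20%. The plan's figure reproduces, and the population rule does not enter it.

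**2. How many patients the rule removes.** The SAP gives only the overall dropout. Assume it is spread evenly over the four visit intervals.

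- 20% of 400 = 80 dropouts, or 80 / 4 = 20 per interval.
- 20 leave before Week 13 (no value) and 20 between Weeks 13 and 26 (one value), so 40 of 400 (10%) are excluded.
- With total dropout of 10% or 30%, the excluded number is 20 or 60, of whom 10 or 30 have exactly one value.

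**3. Size of the bias in a case that can be done by hand.** Assume SD of change 16, true effect 0, and correlation ρ between the Week-13 and Week-52 changes. Patients leave after Week 13 only from the worst 30% at Week 13.

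- The mean of the worst 30% of a normal distribution lies 1.159 SD above the overall mean: 1.159 × 16 = 18.54 points.
- Removing a fraction p of an arm from that group shifts the mean of those kept by −18.54 × p / (1 − p).
- At 10% on NR and 5% on placebo the shifts are −2.06 and −0.98, a difference of −1.08. Carried to Week 52 this is −1.08 × ρ = −0.54 at ρ = 0.5 and −0.76 at ρ = 0.7.
- At 15% and 5% the shifts are −3.27 and −0.98, a difference of −2.30 before rounding: −1.15 at ρ = 0.5 and −1.61 at ρ = 0.7.

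A large simulation of the same cases gave −0.54 and −0.73, then −1.11 and −1.56, on the restricted set. MMRM on all available data gave 0.01 to 0.06. With 5% leaving in each arm, both analyses gave about 0.

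**4. Trial-size simulation.** 400 patients, Week-52 SD of change about 15.4, effect growing linearly to −5 (negative favours NR), 10% leaving between Weeks 13 and 26, and 1500 trials per scenario.

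| Who leaves after Week 13 | MMRM, all patients | MMRM, two or more values |
|---|---|---|
| Worsening patients on placebo, random on NR | −4.95 | −3.89 |
| Worsening patients on NR, random on placebo | −4.92 | −5.90 |
| Same outcome-driven pattern in both arms | −5.02 | −4.96 |
| Random in both arms | −5.04 | −5.03 |

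In the first row power falls from about 85% to 66%. With no true effect, the restricted estimate in the first two rows is off by about 1 point in either direction, and two-sided rejection is about 10% instead of 5%.

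**5. Sensitivity to the assumptions.** With 10% per arm leaving, SD 16 and adjacent-visit correlations of 0.6, 0.75 and 0.85:

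- bias is about 0.4, 0.9 and 1.3 points;
- type I error is about 6%, 7–8% and 11–13%;
- power in the unfavourable direction is about 79%, 70% and 59%.

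A further simulation over other settings gave 0.6 to 1.6 points and 7 to 16% type I error when 10% leave after Week 13, and 0.3 to 0.9 points and 6 to 8% when 5% leave.

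**The case against.** The strongest reply concerns size.

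- **Timing.** The 1-point bias and 10% error need 10% of patients to leave in a single interval, for outcome-related reasons in one arm only. Even spreading of 20% dropout puts 5% there, which gives roughly 0.5 point and 6%. This stands: the 10% case is an upper scenario.
- **Recoverable patients.** About half of the 40 excluded patients have no post-baseline value and add nothing to an MMRM with baseline as covariate. This stands too: about 20 patients matter for the primary test. The other 20 matter for the imputation and for ITT reporting. Requiring one value is not the same fault as requiring two, because a patient with none has no observed follow-up value for the rule to delete.
- **Direction.** If worsening placebo patients leave, the NR effect shrinks and false rejections rarely favour NR (0.6% in one null run, against a nominal 2.5%). A false advantage for NR needs worsening NR patients to leave. This stands: the inflated error is two-sided, and the two directions do different harm.
- **Imputation set.** Section 5.3 names none, so the imputation may already be meant for everyone. What can be said is that the set is unspecified.
- **FAS.** The appendix keeps patients with a missing total. But it does not define the FAS or make it the primary set, so it does not restore them.
- **Week 52 only.** This attendance pattern is uncommon, and the simulations, which use monotone dropout, do not cover it.

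None of this supplies a reason for the rule. It does not reduce bias under missing-at-random, and it discards collected data.

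**Conclusion.** The concern holds and should be fixed before unblinding. The set is a modified ITT set under an ITT label, and its restriction serves no purpose in the specified model. Bias is possible, not certain: near zero if early leaving follows the same pattern in both arms, and from a few tenths of a point to about 1.6 points, against a design effect of 5, if it does not. MMRM on all available data was essentially unbiased in the scenarios run.

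These sizes rest on assumed dropout timing, arm-specific mechanisms and between-visit correlations. The SAP gives only the overall rate. They also read measurements as MDS-UPDRS totals, which section 3.3 does not say. On that reading, section 5.1 adds a further route to exclusion, because one missing item voids a total.

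**What to change.** In SAP section 3.3, define the ITT population as all randomised patients, analysed in the arm allocated, and delete the condition on the number of post-baseline measurements. In section 5.2, state that the MMRM uses every randomised patient with a baseline value and at least one post-baseline MDS-UPDRS total, with all available visits. In section 5.3, state that the reference-based imputation covers all randomised patients, including those with no post-baseline value. In the appendix, define the FAS or replace it with the ITT population, and reconcile its removal of incorrectly randomised patients with the ITT principle. The set with two or more values may stay as a supportive analysis.

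The cost is SAP wording only. No new data are needed, and the planned 162 evaluable and 200 randomised per group are unchanged.
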